8.1.3 SELF-REPORT OF DRUG USE VIA APP

- Participants will be required to install an app on their smartphone, tablet, or similar device which records daily self-reported drug use from Day 1 through Week 32 or the Early Termination visit. The app will query participants daily on their past-day use, upload responses to a database at regular intervals, and notify investigators when participants are non-responsive.

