1.2. Study Design

InterveXion's protocol M200C-2201 is a Phase 2, double-blind, placebo-controlled, multiple-dose study of the safety and efficacy of monthly intravenous (IV) doses of IXT-m200 in treatment-seeking individuals with METH use disorder. The study was stopped before enrolling Cohort 2. As such, any reference to Cohort 2 in this document no longer applies, but has been retained for reference.

The study consists of two cohorts:

- In Cohort 1, approximately 60 participants will be randomized in a 2:1 ratio to IXT-m200 1.5 g or placebo (saline).
- In Cohort 2, approximately 60 participants will be randomized in a 2:1 ratio to the recommended dose of IXT-m200 or placebo based on the interim analysis at the end of Cohort 1. If the interim analysis recommends maintaining a dose of 1.5 g, then the sample size will be recalculated.

In each cohort, participants will receive either study drug (IXT-m200 at the cohort-specific dose or placebo) at the beginning of Weeks 1, 5, 9, 13, 17, and 21. All participants will also participate in seven sessions of a standardized cognitive behavioral therapy (CBT) program which will be delivered by a trained therapist; the first dose of IXT-m200 or placebo is intended to be given on the same day of initiation of CBT. For Cohort 1, the participants will participate in the CBT sessions during their monthly visits. For Cohort 2, participants will go to the clinic weekly for saliva drug tests and will participate in CBT sessions every two weeks, starting with Week 1. Participants will be followed at monthly intervals through Week 33. Cohort 1 will use app-based assessments to monitor between visits and Cohort 2 will use TLFB to monitor between visits. Schema 1.2 in the protocol displays the schematic of the study design for Cohort 1, and Appendix 1 shows the schedule of events. The first four weeks of treatment will be considered a grace period, designed to accommodate the likelihood that participants will relapse initially and experience the effects of IXT-m200. It further allows participants time to absorb and incorporate some of the skills taught by cognitive behavior therapy. METH use endpoints will be analyzed in the weeks following the grace period.

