4.8. Exploratory Analyses

Exploratory analyses will be performed on the ITT population.

Proportion of responders meeting early remission criteria at Week 33

An additional exploratory objective is the proportion of responders at Week 33 as measured by DSM-5 criteria. A responder is a participant who meets the definition of early remission, i.e., \geq 3 months and \leq 12 months without meeting DSM-5 criteria, while disregarding the result for craving. All other criteria, 10 in total, will be counted. Participants that withdraw or discontinue prior to Week 5, or do not have any reported saliva or self-report use data between Weeks 5 and 25 will not be included in the analysis.

The proportion of participants achieving a response will be compared in each IXT-m200 dose group versus the placebo group using a stratified Mantel-Haenszel statistic with stratification

level of past-month METH use at screening (discrete). The output will provide the risk difference between each IXT-m200 dose group and the placebo group, two-sided p-values, and 95% confidence intervals using the Miettinen-Nurminen (score) confidence limits.

Adverse Outcomes

An exploratory objective is to evaluate the efficacy of IXT-m200 in reducing the number of adverse outcomes from the Adverse Outcome Assessment. The assessment will be conducted at Screening, and Weeks 13, 25, and 33. All responses should be counted over the past 3 months. A summary table will provided, showing the mean, standard deviation, median, and min and max for each treatment group, at each of the given weeks. No formal statistical testing will be performed for this endpoint.

Percent of days abstinent from stimulants between Week 5 and Week 25

A secondary objective is to evaluate the efficacy of IXT-m200 in preventing or reducing the relapse to stimulant use, as measured by the percent of days abstinent from stimulants following a 4-week grace period (between Week 5 and Week 25) using self-report surveys via smartphone app.

Participants are to self-report their use/abstinence for each day of the study via the smartphone app. Missing survey data will be imputed assuming a use day. The analysis will be repeated without the imputation of missing data.

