A secondary objective is to evaluate the efficacy of IXT-m200 in improving the proportion of participants achieving stimulant abstinence, defined as complete abstinence during the last scheduled month of study drug treatment (between Week 21 and Week 25), as measured by saliva screens.

A participant will be categorized as fully abstinent if they have zero days of use (between Week 21 and Week 25); otherwise, a participant will be categorized as not abstinent (failure). Participants who withdraw or discontinue prior to Week 5, or do not have any reported saliva or self-report use data between Weeks 5 and 25 will not be included in the analysis.

The proportion of participants achieving a response will be compared in each IXT-m200 group versus the placebo group using a stratified Mantel-Haenszel statistic with stratification level of past-month METH use at screening (discrete). The output will provide the risk difference between each IXT-m200 dose group and the placebo group, two-sided p-values, and 95% confidence intervals using the Miettinen-Nurminen (score) confidence limits.

Reduction in the frequency of METH use over time

An additional exploratory objective is to evaluate the efficacy of IXT-m200 in reducing the frequency of METH use over time. For each day from the start of Week 5 through the end of Week 25, abstinence or use will be based on the self-reported use in the previous seven days. The number of use days in each week will then be determined.

The weekly total for a subject will be derived by counting the number of use days among the non-missing days and normalizing to a seven-day period. For example, for a subject with 1 use day among 4 non-missing days and 3 missing days in a given week, the number of use days (X) will be derived as X = (1/4)*7 = 1.75. No rounding will be performed. If a subject has all missing days in a given week, that week will not be imputed and therefore will not contribute to the analysis.

The number of use days per week will be summarized in a table presenting the mean and standard deviation for each treatment group, at each of the weeks from 5 to 25. No formal statistical testing will be performed for this endpoint. A plot of these group means across weeks will be provided.

[figure not shown]
A spaghetti plot will also be provided to show the use days per week by subject throughout the study. Pseudo-R code for the plot is included in Exhibit 7, and an example of the plot is included in Exhibit 8.

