### RESPID is response ID, a sequential numbering of the dataset observations
### SUBJIDN is an integer valued SUBJID, a sequential numbering of unique subjects
for(i in 1:length(survey$RESPID)) {
 for(j in 1:max(SUBJIDN)) {
  if(survey$SUBJID[i]==startday$SUBJID[j]) {
   survey$DAY[i] <- as.numeric(survey$DATE[i]) - as.numeric(startday$DATE[j])</pre>
   survey$WEEK[i] <- (as.numeric(survey$DAY[i]) %/% 7)+1
   survey$METH01[i] <- as.integer(survey$METH[i]=='Methamphetamine')
   if(is.na(survey$METH01[i])) {survey$METH01[i]=0}
setDT(survey)
weeksdat <- survey[,list(usedays=sum(METH01)), by=.(TRT GRP,SUBJID,WEEK)]

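### SAP 4.8 contradicts itself on how a day is scored for weekly METH use days: one sentence uses a seven-day look-back, while the worked example, the app question and Exhibit 7 use each day's own report

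*SAP*

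**What the plan says.** SAP 4.8, under the heading on reduction in the frequency of METH use over time, gives a day-level rule that covers every day of Weeks 5 to 25: "abstinence or use will be based on the self-reported use in the previous seven days". Use days are then totalled week by week.

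The following paragraph gives the weekly rule, "counting the number of use days among the non-missing days and normalizing to a seven-day period". It illustrates the rule with one case, worded "for a subject with 1 use day among 4 non-missing days and 3 missing days in a given week"; the answer given for this case is 1.75. A week with no reports is left out. The results are a table of means and standard deviations by group and week, a plot of the group means, and a spaghetti plot by participant. There is no formal test.

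Other places bear on how a day is scored:

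- Protocol 8.1.3: "The app will query participants daily on their past-day use".
- SAP 4.8, percent of days abstinent: "Participants are to self-report their use/abstinence for each day of the study via the smartphone app".
- SAP Exhibit 7, the code for the spaghetti plot: "weeksdat <- survey[,list(usedays=sum(METH01)), by=.(TRT GRP,SUBJID,WEEK". It sums a single-day indicator by participant and week, with no look-back.
- SAP 1.2: "METH use endpoints will be analyzed in the weeks following the grace period".

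**The concern.** The sentence is the only place in the text that says how a day becomes a use day for this endpoint. Read as written, it applies a rolling seven-day window to every day and then counts the flagged days, although each day already has its own answer.

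The endpoint is there to show use becoming less frequent without necessarily stopping. A rolling look-back would mask that, because the weekly count reaches its ceiling of 7 as soon as use occurs at least once in every seven days. SAP 4.1 says that the range of endpoints is meant to show how useful each one is for measuring treatment effect. A count stuck at its ceiling would give a misleading answer about this one.

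The window would also reach back behind the grace period. Week 5 starts on Day 29, and a look-back over the seven preceding days scores that day on Days 22 to 28.

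**Working it through.** **1. Reproduce the SAP's example.** The inputs from SAP 4.8 are 1 use day, 4 non-missing days and 3 missing days.

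Weekly count = (use days ÷ non-missing days) × 7 = (1 ÷ 4) × 7 = 1.75.

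With own-day scoring this holds wherever in the week the use day and the missing days fall.

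**2. Apply the look-back to the same week.** Assume that any use in the window makes the day a use day, and that the previous week is fully reported and free of use. There are 35 ways to choose 3 missing days from 7, and 4 reported days on which the use can fall, so 35 × 4 = 140 placements.

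- If a day is missing only when its whole window lacks reports, no day is missing. All 140 placements give whole numbers: 0 to 6 if the window excludes the scored day, 1 to 7 if it includes it. None gives 1.75.
- If a day is instead set to missing whenever its own report is missing, the result depends on where the use falls among the four reported days. The possible scores are 0, 1.75, 3.5 and 5.25 with the window excluding the scored day, or 1.75, 3.5, 5.25 and 7 including it. Each arises in 35 of the 140 placements, so 1.75 appears in 35 ÷ 140 = 25%.

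The SAP obtains 1.75 from the counts alone. That fits own-day scoring in every placement, and the look-back in none or a quarter of them. The sentence does not say how to treat a partly reported window.

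**3. Size if programmed literally.** Assume complete reporting and the any-use rule.

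| Pattern of use | Own-day score per week | Look-back score per week |
|---|---|---|
| One isolated use day (total over all weeks) | 1 | 7 |
| One fixed day each week | 1 | 7 |
| Two days each week | 2 | 7 |
| Three days each week | 3 | 7 |
| Every day | 7 | 7 |
| One day every two weeks (long run) | 7 × 1/14 = 0.5 | 7 × 7/14 = 3.5 |

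The ceiling is reached when the interval between successive use days is never more than seven days. Less frequent use stays below 7.

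**4. A true halving.** Assume also that daily use is independent with probability p. The documents give no figure or model for this.

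Own-day score = 7p. Look-back score = 7 × (1 − (1 − p)^7).

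- p = 0.5: own-day 3.5; look-back 7 × (1 − 0.0078) = 6.95.
- p = 0.25: own-day 1.75; look-back 7 × (1 − 0.1335) = 6.07.

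The true fall is 50%. The look-back shows (6.95 − 6.07) ÷ 6.95 = 13%.

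**5. What governs the outputs.** Exhibit 7 is labelled as code for the spaghetti plot. The SAP gives no code for the table of weekly means or the group-mean plot, so the text governs those. Exhibit 7 also leaves out the scaling to seven days and sets a missing METH indicator to 0, so it cannot stand in as the specification for the table.

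**The case against.** The strongest reply is that the plan's intention is plain. The app question, the daily reports, the worked example and Exhibit 7 all treat the day as the unit, and a programmer who read the whole section would probably score each day on its own report. The sentence never says that any use in the window makes the day a use day; the point-prevalence text in the same section does state an any-positive rule. On a looser reading, the sentence means only that each week draws on that week's seven daily reports. The endpoint is exploratory and descriptive, and self-reported use is also covered by percent of days abstinent, which is tested, and by the curve of participants with n or fewer use days.

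Most of this stands. A reader might infer that the planned endpoint turns one use day into seven and cannot separate weekly from daily use. The documents do not support that: it needs the literal sentence, an unstated any-use rule, and intervals between use days of at most seven days. The grace-period overlap likewise arises only on the literal reading.

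The reply does not remove the contradiction. The sentence is attached to each day, not to each week, so the looser reading has to be supplied by the reader. Exhibit 7 covers one of the three outputs. Two competent programmers could produce different tables, or a table that disagrees with the plot beside it.

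**Conclusion.** The finding is an internal contradiction in an operative derivation rule, and it should be corrected. The evidence favours own-day scoring as the intended rule. The look-back sentence resembles the point-prevalence wording in Protocol 9.4.9 (Table 2) and SAP 4.8, so carry-over is plausible but not shown.

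The inflation figures are conditional: all need the literal sentence and the any-use rule, and the 6.95 to 6.07 comparison also needs independent daily use. What is at risk is one table of weekly means and standard deviations, its group-mean plot, and their agreement with the spaghetti plot. The primary analysis does not use this derivation.

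**What to change.** Replace the sentence in SAP 4.8 with:

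*Each day from the start of Week 5 through the end of Week 25 is a use or non-use day according to the participant's own self-report for that day; days without a report are missing.*

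Keep the seven-day look-back for the point-prevalence endpoint only. The weekly scaling and the worked example can stay as they are.

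In the same edit, say which rule applies after withdrawal. This endpoint leaves fully missing weeks out, while SAP 4.1.2 scores days after withdrawal as not abstinent for self-report endpoints.

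The cost is a short edit to the SAP. It needs no new data and no change to the app.

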IXT-m200 in improving the proportion of participants achieving stimulant abstinence. To evaluate the efficacy of IXT-m200 in reducing the frequency of METH use over time, as measured by self-report. To evaluate the efficacy of IXT-m200 in preventing or reducing relapse to stimulant use, as measured by self-report.	Difference between groups in the trend over time in the number of use days per week, as measured by self-report for Weeks 5 through 25. Proportion of participants with n or fewer use days between Week 5 and Week 25 measured by self-report.
To evaluate the efficacy of IXT-m200 in preventing or reducing relapse to stimulant use, as measured by saliva screens.	Proportion of participants with n or fewer use days between Week 5 and Week 25 measured by saliva screens.

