4.1.2. Other Missing Data, and Data Errors

Any missing values for treatment responder endpoints will be imputed as "non-responder." Missing values for global impressions scales will be imputed as the neutral result of "No Change."

For endpoints related to saliva screens or self-report surveys, if a participant withdraws from the study, all remaining days following withdrawal will be imputed as not abstinent.

Missing values for quality of life, as measured by the Treatment Effectiveness Assessment, will not be imputed. Participants who withdraw or discontinue prior to Week 5, or do not have any reported saliva or self-report use data between Weeks 5 and 25 will not be included in the analysis.

In general, missing and partial dates will be displayed as captured in participant listing displays. For adverse events:

- Missing start day: first of the month will be used unless this is before the start date of study drug; if the partial date is the same month as the first dose of study drug, the treatment start day will be used and the event will be considered treatment-emergent.
- Missing stop day: the last day of the month will be used.
- Completely missing start or end dates will remain missing, with no imputation applied. Time to onset will be missing, and duration will be considered ongoing.

For concomitant medications/medical history:

- If the partial date is a start date, January and 1 will be used for a missing month and missing day, respectively.
- If the partial date is a stop date, December will be used for a missing month, and the end of the month will be used for a missing day (i.e., 28/29/30/31 dependent on the month and year of the partial date).

For pharmacokinetic purposes, missing concentration data will be considered as non-informative and will not be imputed. No concentration estimates will be provided for missing sample values.

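### SAP 4.1.2 and 4.8 treat post-withdrawal weeks of the self-report use-days endpoint differently with no order of precedence, and the Exhibit 7 plot code omits the seven-day scaling

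*SAP*

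**What the plan says.** SAP 1.1, Table 3, lists among the exploratory endpoints: "Difference between groups in the trend over time in the number of use days per week, as measured by self-report for Weeks 5 through 25". SAP 4.8 (reduction in the frequency of METH use over time) plans weekly means and standard deviations by group, a plot of those means and a per-subject spaghetti plot, with no formal test.

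Three places in the SAP bear on missing days for this quantity.

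- **SAP 4.8, partly missing weeks.** The weekly total comes from "counting the number of use days among the non-missing days and normalizing to a seven-day period". The worked example has 1 use day in 4 reported days: "the number of use days (X) will be derived as X = (1/4)*7 = 1.75".
- **SAP 4.8, fully missing weeks.** "If a subject has all missing days in a given week, that week will not be imputed", and so it adds nothing to the weekly mean. Withdrawal is not mentioned.
- **SAP 4.1.2, after withdrawal.** The scope is "For endpoints related to saliva screens or self-report surveys, if a participant withdraws from the study", and the instruction is that "if a participant withdraws from the study, all remaining days following withdrawal will be imputed as not abstinent".

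Exhibit 7, the pseudo-code for the spaghetti plot, builds a daily METH indicator, includes the line "if(is.na(survey$METH01[i])) {survey$METH01[i]=0", and takes a plain sum of the indicator by subject and week. It numbers weeks from each subject's first survey date. SAP 4.1.5 starts Week 1 at randomisation.

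**The concern.** A week that falls wholly after withdrawal has no survey responses. SAP 4.8 leaves it out of the group mean; SAP 4.1.2 counts it as 7 use days. Neither section refers to the other, and nothing says which takes precedence for this endpoint.

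Because no model or test is planned, the weekly means and their plot are the whole result. SAP 2.2 expects dropout of up to 50%, so by the later weeks the choice could apply to a large share of each arm. Two competent programmers could produce different curves, and different gaps between the curves, from the same data.

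The second problem is independent of withdrawal. The spaghetti plot is meant to show the same use days per week, but its code does not apply the scaling that the text requires. The plot and the table would then carry different values for the same participant-week.

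**Working it through.** **1. Reproduce the SAP's worked week.** One use day, four reported days, three missing days (SAP 4.8):

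- X = (use days / reported days) × 7 = (1/4) × 7 = 1.75. This matches the SAP.

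**2. Apply the other instructions to that week.**

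- SAP 4.1.2, if the three missing days follow withdrawal: each is a use day, so (1 + 3)/7 × 7 = 4.0.
- Exhibit 7: an unscaled sum of the daily indicator = 1.

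**3. A full week after withdrawal.**

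- SAP 4.8: not imputed, does not contribute.
- SAP 4.1.2: 7 use days.
- Exhibit 7: no value if the subject has no survey rows that week; 0 if rows exist with an empty METH field.

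**4. Effect on a weekly group mean.** Let d be the share of the arm withdrawn and m the mean use days among those remaining. The 50% comes from SAP 2.2 as an upper dropout figure. Treating it as withdrawal by a given week, the other values of d, and all values of m are assumptions.

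- SAP 4.8: mean = m.
- SAP 4.1.2: mean = (1 − d) × m + 7 × d.

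| d | m | SAP 4.8 | SAP 4.1.2 |
|---|---|---|---|
| 0.3 | 2 | 2.0 | 1.4 + 2.1 = 3.5 |
| 0.4 | 2 | 2.0 | 1.2 + 2.8 = 4.0 |
| 0.5 | 2 | 2.0 | 1.0 + 3.5 = 4.5 |
| 0.5 | 1 | 1.0 | 0.5 + 3.5 = 4.0 |
| 0.5 | 3 | 3.0 | 1.5 + 3.5 = 5.0 |
| 0.5 | 4 | 4.0 | 2.0 + 3.5 = 5.5 |

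The gap between the rules is d × (7 − m). It exists whenever someone has withdrawn and those remaining average under 7 days. It does not require heavier users to leave.

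**5. Effect on the group difference.** Take the same m in both arms, so use among those remaining does not differ.

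- SAP 4.8: m − m = 0.
- SAP 4.1.2: (share withdrawn on active − share withdrawn on placebo) × (7 − m).
- 40% active, 50% placebo, m = 2: (0.4 − 0.5) × 5 = −0.5 day per week.
- 30% active, 50% placebo, m = 2: (0.3 − 0.5) × 5 = −1.0 day per week.

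**The case against.** The strongest reply is that the two sections can be reconciled. Applied in sequence, 4.1.2 fills the days after withdrawal, and 4.8 then deals with gaps while the participant is still on study. Alternatively, 4.8 is the endpoint-specific rule with its own example and overrides 4.1.2, whose heading refers to other missing data. Each reading is workable. A reader might infer that the sections are irreconcilable, or that 4.8 certainly discards every post-withdrawal week; the text does not support either inference. What stands is that the SAP does not choose, and the two readings give different means.

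A reader might also infer that observed-only means are confounded by retention and that scoring 7 use days cures this. Step 5 shows otherwise: with equal use among those remaining, observed-only gives 0 and the imputed rule gives 0.5 day, produced entirely by retention. Observed-only means have their own weakness if those who leave differ from those who stay, but no passage says that heavier users leave. Seven days is also a severe value for a count endpoint. One randomisation stratum is under 18 METH days a month, at most 17/30.4375 × 7 = 3.9 days a week using the month length in SAP 4.1.5. The documents do not make the 7-day rule the evident choice for the main summary.

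On Exhibit 7, it is tempting to say that the code turns missing days into no-use days. The code comments describe the rows as responses, so an empty METH field may mean that methamphetamine was not selected on an answered survey. The SAP does not define it. The week-origin difference bites only when the first survey is late, since self-report is due from Day 1 (protocol 8.1.3). The missing scaling stands on either reading.

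Finally, the endpoint is exploratory and untested, and Exhibit 7 serves a jittered individual plot, not the table of means. Missing-as-use already appears in other self-report analyses in 4.8, and 4.6.2 calls for imputed saliva and self-report analyses to be repeated without imputation. That limits the impact, but it does not say which rule produces this endpoint's main table.

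**Conclusion.** The point holds as an unranked overlap between two rules, together with a coding mismatch. Under the assumed mean of 2 use days among those remaining, the choice of rule moves a weekly mean from 2.0 to 4.5 at 50% withdrawn. It moves the group difference from 0 to 0.5 day at 40% versus 50% withdrawn. These sizes are illustrations: neither the mean among those remaining nor any split of withdrawal by arm is given in the documents.

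The Exhibit 7 discrepancy (1 versus 1.75) rests on no assumption, since it uses the SAP's own worked week. It affects partly missing weeks with at least one reported use day.

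The primary analysis is untouched. The matter should be settled because the means are all this endpoint will report, but its reach is one descriptive exploratory endpoint and its plots.

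**What to change.** In SAP 4.8:

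- State which rule governs weeks after withdrawal, with a cross-reference to 4.1.2, and a matching note in 4.1.2 if this endpoint is exempted.
- Tabulate the weekly means both ways, observed-only and with post-withdrawal days scored as use, with the number contributing per week and arm. Present neither as free of retention effects.
- Keep the seven-day normalisation for partly missing weeks while on study.

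In Exhibit 7:

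- Apply the same normalisation.
- Define an empty METH field: methamphetamine not selected on an answered survey, or no response. Set only the former to 0.
- Count weeks from randomisation, as in SAP 4.1.5.

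The cost is a few sentences of SAP text, a few lines of code and extra columns in one descriptive table. No new data are needed. The SAP introduction allows for amendment before database lock and for documentation in the study report after it.

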4.1.1. Common Statistical Methods and Data Presentations

Descriptive and inferential statistics will summarize results. Unless otherwise indicated, the prespecified efficacy analyses will be conducted using the ITT population. The study will use an overall nominal two-sided Type I error rate of 5%; results will be reported with a two-sided 95% confidence interval (CI) and nominal p-value. For primary and selected secondary and exploratory efficacy outcomes, plots of the cumulative distribution functions (CDFs) will show differences by treatment arm.

Categorical variables will be summarized with the frequency count and percentage of participants with non-missing data. Continuous variables will be summarized using appropriate summary statistics (e.g., the number of non-missing observations, mean, standard deviation (SD), median, 25th and 75th percentiles, minimum, maximum; geometric mean and 95% confidence intervals (CIs) may also be presented, as appropriate).

All summaries will be by treatment group. Tabular presentations will display a separate column for each treatment regimen and graphical summaries will color-code each treatment regimen.

In addition to tabular and graphical summaries, by-participant listings will present all relevant electronic case report form (eCRF) data, sorted by treatment group and participant identifier.

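### SAP Table 3 names a between-group difference in trend for weekly use days, but SAP 4.8 plans no estimate or interval for it

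*SAP*

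**What the plan says.** SAP 1.1, Table 3, defines the endpoint as "Difference between groups in the trend over time in the number of use days per week, as measured by self-report", for Weeks 5 through 25.

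SAP 4.8, under the heading on reduction in frequency of METH use over time, sets out the analysis:

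- The table: "The number of use days per week will be summarized in a table presenting the mean and standard deviation for each treatment group", week by week.
- The test: "No formal statistical testing will be performed for this endpoint".
- The first figure: "A plot of these group means across weeks will be provided".
- The second figure: "A spaghetti plot will also be provided to show the use days per week by subject throughout the study".
- Missing weeks: "If a subject has all missing days in a given week, that week will not be imputed", and the week then contributes nothing.

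Three other places bear on this:

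- SAP 4.1.1 says in general that "results will be reported with a two-sided 95% confidence interval (CI) and nominal p-value".
- SAP 4.1.2 says that, for saliva and self-report endpoints, every day after withdrawal counts as not abstinent. Neither section says which rule prevails for this endpoint.
- SAP 2.2 allows for dropout of up to 50%.

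**The concern.** A difference in trend is a single quantity: the slope in one arm minus the slope in the other. The planned outputs contain neither slope, no contrast and no measure of precision. SAP 4.1 says the range of endpoints is there so that the usefulness of each for measuring treatment effect can be judged. That judgement needs an effect and its uncertainty.

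Readers will look for the trend in the plotted means. Under the 4.8 rule each weekly mean is taken over whoever still reports that week. A line through such means combines change within participants with change in who contributes. If heavier users leave faster in one arm than in the other, the two lines can separate although nobody's use has changed.

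**Working it through.** **1. Endpoint against outputs**

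| Needed for Table 3 | Planned in 4.8 |
|---|---|
| Slope per arm | No |
| Difference in slopes | No |
| Interval for that difference | No |
| Weekly mean and SD per arm | Yes |
| Plot of means; by-subject plot | Yes |

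**2. The SAP's own figure.** The worked example of weekly normalisation is 1 use day among 4 reported days: (1/4) × 7 = 1.75. It reproduces.

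**3. What the means can show.** The documents give no use-day means and no link between use and dropout, so this step is illustrative. Assume half the participants use 1 day per week and half use 5, with no change in any person and no treatment effect. Let r_L and r_H be the proportions of light and heavy users still reporting at Week 25, and R = 0.5 r_L + 0.5 r_H. The Week 5 mean is 3.0. At Week 25:

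- 4.8 rule: mean = (0.5 r_L × 1 + 0.5 r_H × 5) / R
- 4.1.2 rule, reading not abstinent as 7 use days per week: mean = 0.5 r_L × 1 + 0.5 r_H × 5 + (1 − R) × 7

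| Retention, light / heavy | 4.8 rule | 4.1.2 rule |
|---|---|---|
| 50% / 50% | (0.25 + 1.25)/0.5 = 3.0 | 1.5 + 3.5 = 5.0 |
| 60% / 40% | (0.30 + 1.00)/0.5 = 2.6 | 1.3 + 3.5 = 4.8 |
| 70% / 30% | (0.35 + 0.75)/0.5 = 2.2 | 1.1 + 3.5 = 4.6 |
| 30% / 70% | (0.15 + 1.75)/0.5 = 3.8 | 1.9 + 3.5 = 5.4 |
| 80% / 60% | (0.40 + 1.50)/0.7 = 2.7 | 1.9 + 2.1 = 4.0 |

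With 70/30 in one arm and 50/50 in the other, the Week 25 gap under 4.8 is 3.0 − 2.2 = 0.8 use days per week. With 70/30 in both arms it is 0.

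**4. Simulation of the same two-class model** (40 vs 20 participants, 120 trials per scenario, true slope difference 0). The difference is active minus placebo, in slope per week × 20.

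| Dropout pattern | Slopes of 4.8 means | Mixed model with group-by-week |
|---|---|---|
| Placebo 70/30, active 50/50 | 0.0419 × 20 = 0.84 | 0.0013 × 20 = 0.03 |
| Placebo 50/50, active 70/30 | −0.0349 × 20 = −0.70 | −0.0009 × 20 = −0.02 |
| 70/30 in both arms | −0.0017 × 20 = −0.03 | −0.0012 × 20 = −0.02 |

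**5. Simulation with continuous variation** (40 vs 20, 20 weeks, 600 trials per scenario). The assumed SDs are 2 use days per week between persons and 1.2 within persons. The weekly dropout hazard is 0.033 × exp(k × (use − 3.5)); with k = 0, retention is 0.967^20 = 0.51. A person-demeaned slope stands in for the mixed model.

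- Use-related dropout in one arm only: the lines of means differ by about 0.6 (k = 0.3) to 0.9 (k = 0.5) use days per week over the period. The within-person slope difference averages 0.0.
- The same use-related dropout in both arms: 0.05 (k = 0.3) and 0.02 (k = 0.5).
- Dropout unrelated to use: 0.01. Here the SD of the difference is 0.53 from the lines of means and 0.27 from within-person slopes, a variance ratio of (0.27/0.53)² = 0.26.

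**6. Under the 4.1.2 rule.** Withdrawn participants stay in at 7 use days per week. If withdrawal is the only source of missing weeks, the data are then complete, and the slope of the means equals the within-person slope. Neither the bias contrast nor the variance gain in step 5 applies.

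**The case against.** **Descriptive handling is deliberate.** SAP 4.8 declines testing here and also treats adverse outcomes and the two endpoints on n or fewer use days descriptively. Table 3, unlike Table 2, assigns no estimands, and the general sentence in 4.1.1 need not override endpoint-specific text. This stands as a defence of having no p-value. It does not supply the quantity Table 3 names. The n-or-fewer endpoints are worded as proportions, which their planned summaries do deliver.

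**A reader might infer that only weekly means are produced.** That is too strong. SDs and a by-subject plot are planned, and a crude slope difference could be worked out from the tabulated means. No interval could be, and the changing set of contributors would remain. The by-subject plot is also an imperfect guide: the Exhibit 7 code sums use days without the seven-day normalisation, so the SAP's example week would plot as 1, not 1.75.

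**A reader might infer that the plotted trend does reflect who stays in the trial.** The documents do not support that. It is a risk that needs the 4.8 missing-week rule and use-related dropout or non-response that differs between arms. Nothing in the documents says that such a difference will occur.

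**A reader might infer that frequency of use goes unanswered.** It does not. SAP 4.8 compares the percentage of self-reported abstinent days over Weeks 5 to 25, with a 95% CI and p-value. That addresses level, not trend.

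**The model has limits.** A straight line on an outcome bounded at 0 and 7 is a simplification. Dropout driven by unobserved changes in use would bias the model too. Both points stand and should be stated with the result.

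**Conclusion.** The mismatch is real: Table 3 names a between-group difference in trend, and 4.8 plans neither an estimate nor an interval for it. The missing estimator is a defect under either rule for missing weeks. The possible distortion of the plotted lines is conditional. Under 4.8, with about half the participants lost, it is roughly 0.6 to 0.9 use days per week over the period if use-related dropout occurs in one arm only, and about 0 if both arms share the pattern or dropout is unrelated to use. These sizes rest on assumed distributions of use and dropout, because the documents give none. They do not carry over to the 4.1.2 rule, so the conflict between the two rules has to be settled in the same edit. Severity is low: the endpoint is exploratory, untested and tied to no decision.

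**What to change.** In SAP 4.8:

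1. Add a longitudinal model of weekly use days with treatment, week, treatment-by-week, METH-use stratum and a participant random effect, with robust standard errors. Report the difference in slopes over Weeks 5 to 25 with a 95% CI and no formal test. State that the estimate assumes a linear trend and data missing at random.
2. State whether 4.8 or 4.1.2 governs weeks after withdrawal, and run the other rule as a sensitivity analysis.
3. Show the number of participants contributing per arm and week. Keep the table and plots as descriptive support, and bring Exhibit 7 into line with the seven-day normalisation.

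If the sponsor prefers no model, the minimum is to reword the Table 3 endpoint as a descriptive summary of weekly use days by arm; items 2 and 3 still apply.

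The cost is one model on data already derived, one sensitivity run and a few sentences. No new data are needed.
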